#### Catheter Management and Care Documented: Appendix

Number and rate of times that the following best practice indicators were documented

- Department/Unit of catheter insertion
  - Operating Room
  - Bed-side
    - Cardiac Intensive Care Unit (CICU), Surgical Intensive Care Unit (SICU), Medical Intensive Care Unit (MICU)
  - Interventional Radiology
- Personnel performing the insertion
- Physician assistance Advance Practice Nurse

- Catheter insertion site
  - Subclavian
  - Internal jugular
  - Femoral
  - Cephalic vein
  - Basilic vein
  - Brachial vein
- Frequency of dressing changes
- Mask was used during dressing change procedure
- Mask was used during access procedure for CVCs, PICCs, HD catheters
- Accessing central line procedure
- Scrub the hub procedure document
- Alcohol impregnated cap
- CUROS cap
- Frequency of line flushing
- Flush with normal saline as per post infusion policy
- Flush with heparin lock as per post infusion policy
- Syringe size used for flushing documented
- Infusion pump high pressure alarm documented
- Type of products infused through line (medications, etc)

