## **HYPOTHESIS**

There is no statistical significant difference between mechanical/technical, thrombotic, and other adverse outcomes associated with CVCs, PICCs and HD catheters due to variation in insertion and management practices and with adherence to hospital approved EBP guidelines for CVCs, PICCs and HD catheters.

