## **PRIMARY ENDPOINTS**

1. To document number of mechanical/technical, thrombotic, and other adverse outcomes associated with CVCs, PICCs and HD catheters in two groups:
  - 1a. Clinicians interventions and management in adherence with hospital approved EBP guidelines for CVCs, PICCs and HD catheters.
  - 1b. Clinicians interventions and management not in adherence with hospital approved EBP guidelines for CVCs, PICCs and HD catheters.

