## **CASCADE STUDY**

examined using Fisher's exact test or Pearson's Chi-square test, as appropriate.

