#### Key Points

#### Procedure for Pre-Treatment

- Gather Supplies
- Close curtain
- Wash hands using soap and water or hand gel
- Don gloves
- Apply mask to self and patient
- Place 4x4 gauze pads under Tego connector caps. If Tego connector cap is due for change (Weekly) see policy # C-10A.
- Disinfect the arterial cap by scrubbing the hub x 15 vigorous rotations with a Provantics swab.

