
## Appendix C

### CASCADE STUDY DATA COLLECTION TOOL

| Please provide in this format: |            |             |     | Not in this format: |            |                          |     |
|--------------------------------|------------|-------------|-----|---------------------|------------|--------------------------|-----|
| MRN                            | HAR        | Medication  | ... | MRN                 | HAR        | Medication               | ... |
| 1234567                        | 2000000001 | Albuterol   | ... | 1234567             | 2000000001 | Albuterol
Simvastatin | ..  |
| 1234567                        | 2000000001 | Simvastatin | ... |                     |            |                          |     |

| Item  | Values/examples   | Description  |
|---|---|--|
| MRN   | 7 or 9 digit number   | Patient's MRN  |
| HAR   | 10 digit number   | Patient's HAR  |
| Name  | XXX, XXX alphanumeric   | Patient full name  |
| Sex   | Male/Female   | Patient's gender   |
| Age   | Number  | Patient's age at admission (number)  |
| Line, Drain, Airway, Tubes and Wound (LDAW) of the following types: CVC, PICC and PIV             | Include only the following: CVC Double Lumen, CVC Single Lumen, Peripheral IV, PICC Double Lumen, PICC single lumen, PICC Triple Lumen                                  | Specifies the type of LDAW that was placed   |
| Date of LDAW placement  | XX/XX/XXXX X:XX:XX AM/PM  | The date and time the LDAW was placed  |
| Date of LDAW removal  | XX/XX/XXXX X:XX:XX AM/PM  | The date and time the LDAW was removed   |
| Calculated field:
Duration of LDAW  | Number of hours   | This can be calculated by subtracting the LDAW placement date from the LDAW removal date. Please present results to hours.   |
| LDAW Removal Reason   | Discharge, Catheter damage, therapy complete, leaking, occluded, per order, per protocol, purulent drainage, removed by patient, infiltrated, phlebitis, site change, other (comment) | The reason that the LDAW was removed   |
| Calculated field:
Unit in which the LDAW was placed                                     | Any hospital unit name  | This unit can be determined based on the following criteria: the time of LDAW placement falls between admission into this unit AND before transferred out of or is discharged from this unit.  |

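### For care items that recur during dwell, the 1a/1b comparison of complication numbers ignores dwell time and can show a difference when adherence has no effect

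*Combined protocol and SAP*

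**What the plan says.** The primary endpoint is a count: "To document number of mechanical/technical, thrombotic, and other adverse outcomes associated with CVCs, PICCs and HD catheters in two groups", adherent (1a) and non-adherent (1b). The Hypothesis section turns this into a significance question: "There is no statistical significant difference between mechanical/technical, thrombotic, and other adverse outcomes associated with CVCs, PICCs and HD catheters" according to practice variation and adherence.

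The care indicators are introduced as "Number and rate of times that the following best practice indicators were documented". They mix one-time items (insertion site, who inserted the line) with repeated acts: "Frequency of dressing changes", masks at dressing change and at access, hub scrubbing and flushing. The rate mentioned there belongs to documentation of the indicators, not to complications. No rule says how a line with many such acts becomes 1a or 1b.

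Appendix A confirms that care recurs for a sampled device. The dialysis policy R-98 has a weekly item, "If Tego connector cap is due for change (Weekly) see policy # C-10A", and its pre-treatment procedure includes a mask and "Disinfect the arterial cap by scrubbing the hub x 15 vigorous rotations with a Provantics swab".

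Data Analysis lists descriptive summaries, Pearson correlation, t or Wilcoxon tests, ANOVA or Kruskal-Wallis, and categorical variables "examined using Fisher's exact test or Pearson's Chi-square test, as appropriate". Dwell is recorded under Catheter Dwell and derived in Appendix C ("This can be calculated by subtracting the LDAW placement date from the LDAW removal date"), but no stated analysis brings it into the 1a/1b comparison. Nothing limits scoring to care given before the complication. Limitations does not mention dwell.

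**The concern.** Dwell time drives both sides of the comparison. A longer stay means more acts due, so a higher chance that at least one is missed, and more days at risk of a complication. This holds however carefully the abstractor applies the policy. Background and Significance shows that intended dwell varies widely: days or weeks for non-tunneled lines, weeks or months for PICCs, months or years for tunneled CVCs.

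The path can also run the other way. A complication that leads to removal shortens dwell and leaves fewer acts to miss. Appendix C allows for both courses: alteplase given while the line stays in, and removal because the line is occluded or leaking.

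At stake is the primary association. It could be reported as significant, in either direction, without any effect of adherence, and the Benefits section says the data will be used to design a prospective study.

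**Working it through.** **Inputs.** From the documents: 300 records (175 + 75 + 50), no event rate, power or effect size, so there is no planned figure to reproduce. The only dressing interval printed in Appendix A is 7 days, for apheresis catheters. Assumed, because the documents give none: miss rate, dwell distribution, complication rate, the any-miss rule, and a weekly item.

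**Step 1: chance of entering 1b.** With *k* acts due and a share *m* missed, P(at least one miss) = 1 − (1 − m)^k.

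| k | m = 5% | m = 10% | m = 20% |
|---|---|---|---|
| 1 | 5.0% | 10.0% | 20.0% |
| 2 | 9.8% | 19.0% | 36.0% |
| 3 | 14.3% | 27.1% | 48.8% |

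**Step 2: hand example with no effect of adherence and lines kept in.** Take 150 lines in for 7 days and 150 for 21 days, with 1% complications per day. Risks are 1 − exp(−0.07) = 6.76% and 1 − exp(−0.21) = 18.94%.

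- Removal day not counted as due (0 and 2 acts), m = 20%: 1b holds 150 × 36% = 54 lines, all 21-day, risk 18.94%. 1a has 150 × 6.76% + 96 × 18.94% = 28.3 events in 246 lines, 11.5%. Ratio 1.65 (1.66 to 1.61 for 0.5% to 2% per day).
- Removal day counted (1 and 3 acts), m = 20%: 1b has 30 × 6.76% + 73.2 × 18.94% = 15.9 events in 103.2 lines, 15.4%. 1a has 120 × 6.76% + 76.8 × 18.94% = 22.7 in 196.8, 11.5%. Ratio 1.34.
- Removal day not counted, m = 5%: 1b holds 150 × 9.75% = 14.6 lines at 18.94%. 1a has 150 × 6.76% + 135.4 × 18.94% = 35.8 in 285.4, 12.5%. Ratio 1.51.

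**Step 3: simulation of the planned test with a true ratio of 1.** 300 lines; gamma dwell (shape 2) with mean 7 or 14 days; constant hazard giving 10% or 20% complications; weekly item, removal day not counted; 5% to 20% missed independently of complications; any miss = 1b; chi-square, or Fisher where an expected count is below 5.

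| Complications that end the line | Risk ratio | Rejections at nominal 5% |
|---|---|---|
| None | about 1.6 to 1.9 | 13% to 61% |
| Half | about 1.1 to 1.3 | 3% to 13% |
| All | below 1 | 0% to 21% |

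Dwell shape matters. A separate run used lognormal dwell (log SD 0.8, median 7 or 14 days), 5 or 10 complications per 1,000 catheter-days, 10% or 20% missed and no line-ending events. It gave median ratios of 1.9 to 2.4 and Fisher rejection of 22% to 75%.

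**Step 4: the grouping rule.** In that lognormal run, calling a line 1b when more than 20% of due acts are missed, with none-due lines kept as adherent, gave ratios of 1.3 to 2.1 and 8% to 34% rejection. Requiring at least 80% of due acts done, with none-due lines left out, gave 1% to 18% under gamma dwell.

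**Step 5: candidate analyses.** Dividing by catheter-days using each line's final group gave about 3% to 5% rejection when no complication ends the line, but up to 94% when complications do. The reason is that a line must survive to its first missed act to enter 1b, and those event-free days are then credited to 1b. Splitting each line's days at the first missed act, stratified by week and ignoring later misses, gave 2% to 5% in the Step 3 scenarios. In a wider set of 36 (gamma shape 1 or 2, up to 30% complications) it gave 3% to 8%, and again 3% to 8% with a rising hazard.

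**The case against.** The strongest reply is that the size rests on a rule the protocol never states. Any-miss is an assumption. The indicators are to be reported as a rate as well as a number, so scoring per opportunity is a natural reading, and with none-due lines left out it makes the bias much smaller. This stands as a limit on size. It does not remove the point, because the rate does not extend to complications, and a proportion rule that keeps none-due lines as adherent still inflates the error.

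The weekly schedule is also assumed. The CVC, PICC and HD policies are only excerpted, and the weekly R-98 item is a cap change, which is not a listed indicator. That stands too. Masks and hub scrubbing recur with access and are listed, but they were not simulated.

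Direction is not established either. A reader might infer that the plan will make non-adherence look harmful. The documents do not support this, since the removal reasons in Appendix C include occlusion and leaking, and where such events end the line the ratio falls below 1.

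Finally, the stated objective is exploratory, and Limitations concedes that a non-experimental design restricts inference about adherence. That lowers the stakes, but a significance hypothesis is still posed and dwell is not among the stated limitations.

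**Conclusion.** The concern holds for recurring items. Dwell affects both the chance of being classed 1b and the chance of a complication, and the planned tests ignore it although it is collected. One-time insertion items are not affected.

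The size is conditional. Under the Step 3 assumptions, rejection at a nominal 5% ranges from well above nominal when lines stay in to close to or below nominal when half or all complications end the line and few acts are missed. With a per-opportunity rule and none-due lines left out, the bias is small.

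A reader might go further and conclude that false positives approach 100%. Figures of that order come only from combining no line-ending complications, 20% missed, the any-miss rule and less favourable dwell or complication assumptions; nothing in the documents establishes that combination. What is supported is that a significant or null 1a/1b result on recurring items could not be attributed to adherence. The change should be made; confidence is medium because the deciding inputs are unknown.

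**What to change.** For recurring items that can be dated from the flow sheets, at least dressing changes, and for each item separately:

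1. Derive due dates from the insertion date and the policy for that device.
2. Follow each line from insertion to first complication or removal, and ignore misses after the complication.
3. Count catheter-days as 1a until the first missed due act and as 1b afterwards.
4. Report complications per 1,000 catheter-days in 1a and 1b time, and compare them with a Mantel-Haenszel rate ratio stratified by week since insertion and catheter type.
5. Do not simply divide by catheter-days using each line's final group (Step 5).
6. For lines in place on arrival, an option on the Appendix B form, start follow-up at admission, or code the line as not classifiable if its insertion date is unknown. Report the share that cannot be classified.

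Keep the plain two-group table for one-time insertion items.

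The cost is mainly abstraction. Insertion and removal times are already planned, but the Appendix C field list has no dates for dressing changes, flushes or hub scrubs, and its device list omits HD catheters, so fields must be added. The work is modest for weekly acts and heavy for flushing or access. Precision falls because less time counts as 1b, and incomplete documentation will leave some lines unclassifiable.

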## **SECONDARY OBJECTIVE**

1. To explore variation in practices in clinician management of CVCs, PICCs, and HD catheters and non-adherence to hospital approved EBP guidelines and catheter complications.

## **SECONDARY ENDPOINTS**

1. To document number of variation in practices in clinician management of CVCs, PICCs, and HD catheters associated with CVCs, PICCs and HD catheters in two groups:

### Catheter Complication –Appendix B

#### **Mechanical Complication**

- Pneumothorax
- Air embolism
- Catheter occlusion
- Thrombosis
- Pinch-off syndrome
- Catheter malposition
- Catheter rupture

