## BACKGROUND AND SIGNIFICANCE

Central lines have no absolute placement contraindications. They afford a readily available vascular pathway for life-sustaining intravenous fluids, nutrition and medications,

repeated laboratory tests, high-flow infusions, hemodialysis, and hemodynamic monitoring that cannot be precisely measured via non-invasive means. A major factor in the choice of a central access is the intended need. A non-tunneled catheter is the best option for short-term use (days to weeks), PICCs for intermediate use (weeks to months), and tunneled CVCs for long-term care (months to years). At times when vesicant and vasoactive medications are required to avoid local tissue injury or when needed for extracorporeal therapies, central access becomes the only viable alternative. Central lines are categorized as either inserted centrally or peripherally inserted. PICC has become increasingly popular because they are easy to insert, is considered cost-effective, and has been perceived to be safe in comparison to CVCs. PICCs, however, is not without complications. Some of these complications include catheter fracture, leakage, infection, superficial and deep vein thrombosis (DVT). As with all invasive procedures, catheter-use has high probabilities for complications. With more than five million catheters inserted annually, the vulnerability of CVCs to complications mandates a careful, structured investigation from the time of insertion, during dwell time, and at removal. Central venous catheters, now commonplace in critical care, hemodialysis, and long-term care setting, requires specialized knowledge in care, management, maintenance, and documentation. Practitioners, care providers, manufacturers, and regulatory agencies have long recognized that central lines are problem prone. Mechanical, thrombotic, and infectious complications remain the leading cause of catheter malfunction and failure. The hydrophobic surface of CVCs promotes adsorption of protein and cellular adhesions, making them susceptible to thrombotic occlusion and fibrin sheath formation in as early as twenty-four hours after placement. These building blocks eventually precipitate obstruction, a frequent complication of central lines.

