Catheter occlusion occurs within one to two years in approximately 14% to 36%, which can be due to mechanical causes, precipitation of TPN, and low pH medications. Occlusions interrupt and delay patient care, a compromise that often leads to cancellation of life-sustaining therapies, ultimately contributing to mortality and higher overall costs. Occlusions do not just impede critical treatment; they also result in infectious complications due to the formation of complex biofilms of bacteria, viruses, and fungi, an eventuality that situates the supposedly beneficial catheter as the source of problematic bloodstream infections and hospital acquired complications (HAC). Blood stream infections can exacerbate a patients' condition, especially when the patient is immunocompromised, as biofilms are difficult to eradicate due to its high resistance to host defenses and antimicrobials. Catheter-related infection is a serious complication leading to sepsis, septic shock, and a mortality rate as high as 25%. By many analyses, the cost of infectious complications is significant as it increases morbidity, mortality, length of stay, and financial resources. The Centers for Disease Control and Prevention (CDC) approximates the added cost per infection to be at \$16,550 therefore independently escalating hospital length of stay and cost. As a result, catheter utility should be measured by the improvement in a patient's condition relative to its use. Identifying variability in catheter function and the inverse proportionality relative to cost is critical in the current value-based purchasing reimbursement environment. Compounding this issue of economics in catheter management, the Centers for Medicare and Medicare Services (CMS) no longer reimburses for hospital-acquired central line-associated blood stream infections (CLABSI), a never event.

The second highest occurring never event in healthcare is central venous catheter infection, a clearly identifiable, measurable, and preventable HAC. Catheter-related complications are not only detrimental to a good prognosis but is also unacceptable to care

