## **PRIMARY OBJECTIVE**

1. To explore the association between mechanical/technical, thrombotic, and other adverse outcomes associated with CVCs, PICCs and HD catheters due to variation in insertion and management practices and with adherence to hospital approved EBP guidelines for CVCs, PICCs and HD catheters.

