#### **Thrombotic Complication**

- Thrombotic occlusion
- Catheter patency rate
- Drug precipitates

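### The printed complication lists contradict the protocol's own split between mechanical and thrombotic complications, and let one clotted catheter be entered under up to three items

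*Combined protocol and SAP*

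**What the plan says.** Background and Significance treats the classes as distinct: "Mechanical, thrombotic, and infectious complications remain the leading cause of catheter malfunction and failure". It attributes thrombotic occlusion to protein and cells adhering to the catheter surface. On occlusion in general, it says "which can be due to mechanical causes, precipitation of TPN, and low pH medications".

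The itemised lists stand under Secondary Endpoints, Catheter Complication, whose heading points to Appendix B. The mechanical list has seven items, among them "Catheter occlusion" and thrombosis. The thrombotic list has three: "Thrombotic occlusion", "Catheter patency rate" and "Drug precipitates".

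Similar class names appear in the Primary Objective ("To explore the association between mechanical/technical, thrombotic, and other adverse outcomes") and in the Primary Endpoints ("To document number of mechanical/technical, thrombotic, and other adverse outcomes associated with CVCs, PICCs and HD catheters in two groups"). Neither refers to the lists. The Data Analysis section does not say whether the classes are compared separately or pooled. Appendix C records occlusion as a removal reason without a cause, and alteplase use while the line was in place as yes or no.

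**The concern.** An abstractor who follows the lists as printed would file a clot under Mechanical and a drug precipitate under Thrombotic. A blocked catheter could go under either class, or both. The class totals would then not be what their names say.

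There is a second problem. The Primary Endpoints ask for a number of outcomes, and the readable text has no rule that an event is entered only once. A single clotted catheter could therefore add more than one to the total.

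The results are meant to help design a prospective study (Benefits), so unclear outcome classes would carry forward. No other readable part of the plan itemises the mechanical and thrombotic classes.

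**Working it through.** The plan states no figure on this point. The check is a count of the printed items and a comparison with the protocol's own account of causes.

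**Step 1: count.** 7 mechanical + 3 thrombotic = 10 items.

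**Step 2: compare each doubtful item with Background and Significance.**

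| Item | Printed class | Finding |
|---|---|---|
| Thrombosis | Mechanical | A clot event, although the protocol has a separate thrombotic class |
| Catheter occlusion | Mechanical | No cause stated, so as printed it includes thrombotic occlusion |
| Drug precipitates | Thrombotic | Background gives precipitation as a cause of occlusion beside mechanical causes and does not link it to clot |
| Catheter patency rate | Thrombotic | A measure, not an event |

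That is 1 + 1 + 1 + 1 = 4 items affected, which leaves 10 − 4 = 6. Five of these are mechanical (pneumothorax, air embolism, pinch-off, malposition, rupture). One is thrombotic (thrombotic occlusion). So only 1 of the 3 items in the thrombotic list is a clot event.

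**Step 3: multiple entry.** Let T be the number of catheters blocked by clot.

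- Each entered once, as thrombotic occlusion: mechanical 0, thrombotic T, total T.
- Each entered under every item that fits (catheter occlusion, thrombosis, thrombotic occlusion): mechanical 2T, thrombotic T, total 3T.

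The excess in the total is therefore between 0 and 2T. The upper end requires thrombosis to be read as including clot in the catheter. If it means only clot in the vein, a clotted catheter fits two items and the excess is at most T. The documents do not give T.

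**Step 4: which summaries are affected.**

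- Class counts: affected by the misplaced items, by multiple entry and by the patency item.
- Total number of outcomes: not changed by moving items between classes, but affected by multiple entry and by the patency item.
- Any complication, yes or no per catheter: not affected by class or by multiple entry, but only if patency rate is left out of the indicator.

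**Step 5: can the effect be sized?** The only occlusion frequency in the protocol is 14% to 36% within one to two years (Background and Significance). It is not split by cause, and the plan does not tie that period to the dwell times of the sampled catheters. The size cannot be derived.

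**Step 6: does a consistent regrouping exist?** Yes, for example: thrombotic 2 (thrombosis, thrombotic occlusion), non-thrombotic 7 (the five unaffected mechanical items, occlusion of non-thrombotic cause, precipitates), and patency rate on its own. 2 + 7 + 1 = 10.

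**The case against.** No text defines the classes as clot against non-clot. Background and Significance names three classes and lists causes of occlusion, but does not say which class precipitates belong to. This stands: the right place for precipitates is arguable. What the text does not support is a place under Thrombotic.

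The heading above the mechanical list may itself limit the occlusion item to mechanical causes. That would be persuasive if thrombosis were not under the same heading. Background also describes clot and fibrin build-up as leading to obstruction, so the protocol does not confine obstruction to mechanical causes.

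Appendix B is cited for these items and cannot be read here. It may hold definitions that settle the overlap. This also stands, and the overlap is the part most exposed to it. The printed lists would still need to agree with any such definitions.

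A reader might infer that the primary endpoint is wrongly built. The documents do not show that. The Primary Endpoints use slightly different labels, have no infectious class and do not refer to these lists. The link rests on shared class names.

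A reader might also infer that the comparison between adherence groups is biased. The documents do not support that either. They state no clot-only quantity to be estimated and do not say that the classes are compared separately. Suppose the adherent to non-adherent ratio is c for clot events and r for precipitates, and precipitates are a share q of the non-adherent thrombotic count. The observed ratio is then c(1 − q) + rq. This equals c when r = c, and otherwise moves in either direction. None of c, r and q is in the documents.

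**Conclusion.** The inconsistency is real on the printed text, and it is minor. If the lists are followed as they stand, the thrombotic count omits thrombosis, includes a cause that the protocol does not link to clot, and carries a rate among its complications. One clotted catheter can be entered under up to three items, which inflates a count of the number of outcomes.

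The finding that 4 of 10 items are affected comes directly from the documents. No size for the effect on results does. The conclusion assumes that Appendix B holds no rule that overrides the lists. Its reach to the primary endpoint assumes that the shared class names mean the same classes. The study is exploratory, which further limits the weight of the point.

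**What to change.** - Move thrombosis to the thrombotic list.
- Limit the mechanical item to non-thrombotic occlusion.
- Take drug precipitates out of the thrombotic list and report them as non-thrombotic occlusion or on their own line.
- State that each event is assigned to one class, once. Add a category for occlusion with cause not documented, for use where the notes do not show the cause.
- Report patency rate apart from the complication counts, and leave it out of any per-catheter complication indicator.
- Check the revised lists against Appendix B so that the two agree.

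The cost is some rewording and one cause-of-occlusion field. Appendix C cannot supply the cause: its removal reason gives none, and alteplase use does not establish one. It would have to come from the notes and tests already under review (Methodology), with a little extra abstraction time. Some occlusions will remain unclassified. Item-level frequencies, which the Data Analysis section already allows, would show the misplaced labels at no extra cost, but would not resolve occlusions entered without a cause.
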